fMRI data will be collected using a gradient echo-planar imaging sequence. Participants will undergo a 5-minute resting-state scan at first, being instructed to relax with their eyes open, followed by a 5-minute event-design ‘target among distractors’ visual search task. For the task, participants fixate on a black screen for a constant inter-stimulus interval of 1000ms, follow by 5500ms presentation of the search pattern. Participants’ task is to search for target symbol “申” (which was present for 50% of trials), shown among 6 distractors (e.g., “由”, “甲”, etc.). Participants are instructed to press one of two response buttons to indicate whether the target was present or absent.

Secondary endpoints:

- Study partner-rated NPS (frequency and severity scores from NPI and NPI-Q⁴⁶).

Other measures:

- Cognitive functions will be measured using tests from three different versions of the computer-based battery Executive Abilities: Measures and Instruments for Neurobehavioral Evaluation and Research (EXAMINER);
- Paper-based measures of cognitive functioning will be measured using two versions of the Rey Auditory Verbal Learning Test (RAVLT, Lists A&B and C&D) and the Brief Visuospatial Memory

Test-Revised (BVMT-R, Forms 1-3);

- Functioning in daily life will be measured with the self-report version of the Activities of Daily Living-Prevention Instrument (ADL-PI-self).
- Fatigue across 5 domains (general, physical, mental, and reduced motivation & reduced activity) will be measured using the Multidimensional Fatigue Inventory (MFI);
- Sleep habits and quality of sleep will be measured using the total score from the Pittsburgh Sleep Quality Index (PSQI);
- Depression will be measured using both the 15- and 30-item versions of the Geriatric Depression Scale (GDS);
- Risk of suicide (current & past) and current suicidal ideation will be measured using Columbia Suicide Severity Rating Scale (C-SSRS);
- Anxiety will be measured using both the state and trait anxiety scales from the State-Trait Anxiety Inventory (STA);
- Perception of stress will be measured using Perceived Stress Scale (PSS);
- Apathy will be measured using the 18-item self-report and informant-rated Apathy Evaluation Scales (AES);
- Quality of life (QoL) across multiple life domains (including physical health, mood, relationships, activities, ability to perform tasks) will be measured using the 13-item self-report and informant-rated Quality of Life in Alzheimer's Disease scales (QOLAD);

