Assessments: Fully eligible participants and their study partner subjects will be notified of their eligibility for the study. Baseline assessments need to be scheduled within one month of in-person cognitive screening. Participants will then be asked to complete baseline measures (assessment, MRI scan, and blood draw), after which they will be randomized to either the active or sham tDCS intervention condition. The blood draw may occur within 2 weeks (before or after) the baseline assessment and MRI scan. The beginning of the intervention phase will start within two weeks after the baseline assessment and blood draw. Follow-up cognitive assessments and MRI scans for each participant will occur within 2 weeks after completion of intervention (i.e., post-intervention assessment) and then 4 weeks after post-intervention assessment (i.e., follow-up assessment). We will allow 2 weeks to make up the follow-up assessment. At the same time points, study partner subjects will be administered the NPI, AES, and QOLAD. Follow-up assessments for study partners can also be conducted over the phone, at the partners discretion.

A detailed overview of data collection measures for screening and assessments can be found below in **Table 1**. To reduce the burden on participants, study partner subjects, and staff, as well as to avoid practice effects of cognitive measures, for individuals who are eligible for the study, their screening data will be used as baseline data; for those who are not eligible for the study, their screening data will only be used for summarizing the reasons for ineligibility.

Group assignment/randomization will be determined with a block-based matlab randomization.

Table 1: Study Measures I = intervention subject; P = partner subject

	Screening		Baseline	Interventions				Makeup Interventions (if needed)		Post-Intervention Assessments	
	Phone	In-Person		Week 1	Week 2	Week 3	Week 4	Week 5	Week 6	Immediate Post-Intervention	Final Post-Intervention
Study Activities											
Verbal Consent for Screening	I, P										
Inclusion/Exclusion (verified at In-Person)	I, P	I, P									
MRI Screening Form	I										
Informed Consent		I, P									
UBACC		I									
Demographics & background		I, P									
MoCA (V2)		I									
RAVLT		I (Lists C&D)								I (Lists A&B)	I (Lists C&D)
ADL-PI-self		I								I	I
PSS		I								I	I
PSQI		I								I	I
MFI		I								I	I
GDS-15		I		I	I	I	I	I	I		
AES		I, P								I, P	I, P
QoL-AD		I, P								I, P	I, P

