The interventionists will ask every intervention subject’s study partner subject to complete the NPI-Q weekly during the intervention period to monitor changes in NPS among the intervention subjects during the 4-week tDCS sessions. If any symptoms worsen over the intervention period and a worsening is confirmed by the study partner subject, it will be reported as an adverse event (in accordance with reporting procedures described in Section 16). The intervention will then be discontinued. Our co-I, [name], who is a geriatric psychiatrist, will be notified and provide medical assessment and further advice for medical assistance.

Device-Specific Risk Minimization:

Soterix Medical outlines the same risks and risk control features for both devices, tES Model 2001 and tDCS Model 1300A, as follows:

Irritation

- The applied current may cause minor irritation, discomfort, and/or redness at the electrode sites.
- Soterix Medical *EASYPad*™ electrodes should not be placed over previously irritated, burnt, or damaged skin.

Methods of Risk Minimization:

- **SMARTscan™**: a visual 20 bar LED display (1 to 20 from left to right) that indicates to the

operator the contact conditions of the electrodes before, during, and after stimulation. LED 1 denotes short condition and LED 2 denotes open-circuit condition. Stimulation should not begin if either LED 1 or LED 2 is lit.

- **PRE-STIM TICKLE:** a pre-stimulation feature that conditions the skin prior to full stimulation,
- **RELAX:** a feature that allows the operator to decrease the set level of current from the maximum (FULL CURRENT) value to accommodate subject feedback at any point without aborting the stimulation session.
- **TRUE CURRENT™** display is active whenever the device is on and indicates the actual value of current (in mA) being supplied from the device to the electrodes, regardless of device settings. This feature functions as a fully independent and redundant safety feature when monitored by the operator.

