H2a. After intervention, the active, relative to sham group will have greater improvement in study partner-rated NPS in terms of lower severity and fewer co-existing symptoms: We will fit linear mixed-effect models for changes in NPS: $Y_i = X_i\beta + Z_iu_i + \epsilon_i$, where $Y_i = (y_{i1}, \dots, y_{iT})$ represents the NPI measures across time, X_i is a $T \times p$ design matrix for the fixed effects and Z_i is a $T \times q$ matrix for the random effects. The models will include fixed effects such as data collection visit (categorical variable), group, visit and group interaction, and covariates identified as being imbalanced among groups. Stepwise variable selection based on Akaike Information Criteria will be used to select the fixed effects for inclusion. A random participant-specific effect will be included to account for correlation between visits for the same participant. The model-based average within-group change will be computed for each outcome at 4 and 8 weeks. This will allow us to rank the groups in terms of average within-person gains in each outcome. We will conduct a composite hypothesis test to assess if the changes at 4 or 8 weeks differ by groups (similar to a one-factor ANOVA but accounting for repeated measures). **H2b. FC change in NPS-shared neural circuit will contribute to the improvement in study partner-rated NPS across groups:** We will perform epsilon-intensive support vector regression (SVR) with RBF kernel using LIBSVM library.⁵² The Leave-One-Out-Cross-Validation scheme will be applied: each intervention subject will be designated as

the test sample once, while the remaining intervention subjects will be used as training sample. All training sample's features (change of voxel activation from the task or change of FCs from the NPS-shared neural circuit after intervention) will be trained to predict the test sample's outcome (change of NPI severity or frequency score). We will then perform model fitting of the raw and predicted NPI using linear function ($f(x)=ax+b$). Adjusted R^2 will be used to estimate goodness of fit for the model.

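### The AIC stepwise rule for H2a does not exempt visit-by-group, so it can remove the between-group change in NPS that the same paragraph must rank and test

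*Combined protocol and SAP*

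**What the plan says.** Section 17 (Data Analysis Plan), Aim 2, H2a, specifies a linear mixed model for the NPI measures over time with a random participant effect. The fixed effects come in one list: visit as a categorical variable, group, and "visit and group interaction, and covariates identified as being imbalanced among groups". The next sentence is the selection rule: "Stepwise variable selection based on Akaike Information Criteria will be used to select the fixed effects for inclusion". No sentence there or elsewhere names a fixed effect that must stay in.

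The same paragraph then asks for three outputs:

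- Change within each arm: "The model-based average within-group change will be computed for each outcome at 4 and 8 weeks".
- A ranking: "This will allow us to rank the groups in terms of average within-person gains in each outcome".
- A joint test: "We will conduct a composite hypothesis test to assess if the changes at 4 or 8 weeks differ by groups".

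Section 4 names the outcome as a secondary endpoint: "Study partner-rated NPS (frequency and severity scores from NPI and NPI-Q"). On timing, Section 8 says of the post-intervention and follow-up visits: "At the same time points, study partner subjects will be administered the NPI, AES, and QOLAD". Section 9 has partners "complete the NPI-Q weekly during the intervention period to monitor changes in NPS among the intervention subjects". Table 1 places the NPI-Q at phone screening and weeks 1-4 only, so the NPI-Q cannot supply an 8-week change.

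**The concern.** In a model for NPI scores over time, visit-by-group is the only term that lets the two arms change by different amounts. It is the treatment effect for H2a. The selection rule is worded to cover all the fixed effects, so it covers this one.

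If AIC removes the term, change can still be computed from the visit effect, but it is forced to be equal in both arms. The ranking becomes a tie, and the selected model has no parameter for the composite test. If AIC keeps the term, the reported estimate has passed a filter that favours large values, and its ordinary confidence interval ignores that filter.

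What is at stake is the estimate and interval for a secondary endpoint. Section 17 says the pilot's results will inform effect size for a later trial. It names no endpoint there, but an estimate that is missing when small and too large when present would serve that purpose badly.

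**Working it through.** The plan gives no sample size, power or effect size for H2a, so there is no stated figure to reproduce.

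**Inputs from the documents.** Two arms and three assessments: baseline, post-intervention and follow-up (Section 4). Total 40, attrition 10%, alpha 0.05 (Section 17). Completers: 40 × (1 − 0.10) = 36, or 18 per arm if allocation is 1:1. Without attrition, 20 per arm.

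**Assumed, because the documents do not say.** 1:1 allocation, normal outcomes with total SD 1, complete data, random-intercept correlation 0.3, 0.5 or 0.7, the same true effect at both follow-ups, and effects from 0 to 0.9 SD.

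**Step 1: the threshold.** Degrees of freedom for visit-by-group = (3 − 1)(2 − 1) = 2. AIC = −2 log L + 2k, so removing the term lowers AIC when LR < 2 × 2 = 4. P(chi-square on 2 df > 4) = exp(−2) = 0.135. With no true effect, the large-sample chance of removal is 1 − 0.135 = 0.865.

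**Step 2: removal against power.** From the noncentral chi-square on 2 df, if the full-model 5% test has power 30%, 50%, 80% or 90%, the term is removed with probability 51.8%, 31.8%, 9.5% or 4.0%.

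**Step 3: simulation at this trial's size.** 40,000 trials per setting, maximum likelihood, term kept if LR > 4. Estimate and coverage are for the first follow-up contrast. Ranges run over 18-20 per arm and the three correlations.

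| True effect (SD) | Term dropped | Mean estimate when kept (SD) | 95% CI coverage when kept |
|---|---|---|---|
| 0 | 85% | – | 66-68% |
| 0.3 | 59-74% | 0.47-0.60 | 86-93% |
| 0.5 | 26-57% | 0.59-0.77 | 92-96% |
| 0.8 | 2-28% | 0.81-0.94 | – |
| 0.9 | 1-19% | 0.91-1.01 | – |

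A dash marks a figure not tabulated. With the term always kept, the mean is within 0.005 SD of the truth and coverage is 95%. A separate simulation (6,000 trials per setting, correlation 0.5 and 0.7) gave removal in 84-86%, 60-70%, 27-48% and 2-16% at 0, 0.3, 0.5 and 0.8 SD, which agrees.

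**Step 4: what is lost on removal.** At a true 0.3 SD, the interval that would go unreported has an upper limit of 0.5 SD or more in 82-93% of the dropped trials. The fitted model meanwhile shows identical change in both arms. Of the non-significant trials at 0.3 SD, 78-85% would have the term removed.

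**Step 5: the 5% decision.** The 2-df critical value is 5.99, above 4, so any significant result also passes AIC. In 30 settings × 40,000 = 1,200,000 trials, none was significant at 5% but dropped. If removal counts as non-rejection, the overall error rate is unchanged. If the test were reported only when the term is kept, then with no true effect about 0.05 / 0.135 = 37% of the reported tests would be significant.

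**Step 6: sensitivity.**

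- *Effect halved at the second follow-up* (20,000 trials per setting): dropped in 65-77%, 37-63% and 7-37%, with kept means 0.52-0.65, 0.63-0.84 and 0.84-1.02 SD, at true 0.3, 0.5 and 0.8 SD.
- *NPI-Q modelled on its own schedule* (five occasions, 4 df): AIC needs LR > 8 (p = 0.092). The term is dropped in 89-90%, 69-82%, 36-68% and 4-36% at 0, 0.3, 0.5 and 0.8 SD. The 5% decision again does not change.

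**The case against.** The strongest reply is that AIC was meant only to prune covariates. The list is introduced as what the models will contain, the three outputs are promised without condition, and reading the rule as covariate-only keeps every sentence workable. That may well be the intent, and if so the harm is nil. But the covariates stand in the same list as the design terms. Wording that protects the interaction protects the covariates equally and leaves AIC nothing to select. The text does not settle it.

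Second, the paragraph also speaks of modelling changes in NPS and likens the test to a one-way ANOVA. If the response were change from baseline, the group term would carry the treatment difference, and the 2-df figures would not apply. However, the paragraph defines the response as the NPI measures across time. Even on the change-score reading, AIC lost every group term in 79-80%, 46-65%, 16-45% and 1-16% of simulated trials at 0, 0.3, 0.5 and 0.8 SD. The problem is generally smaller for real effects but does not go away.

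Third, AIC has to fit the model with the interaction in order to compare it, so the estimate exists at that point. This is fair: the loss is in what the selected model reports, not in what the data can estimate. The plan does not say that results will be taken from the full model.

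Fourth, the endpoint is secondary, the 5% decision is unaffected, and every magnitude rests on assumptions. NPI scores are bounded and may be skewed, which the simulation ignores. All of this stands and limits the weight of the point.

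**Conclusion.** The concern holds. As written, the rule can remove the only term that carries the H2a treatment difference, and the same paragraph then requires that difference to be ranked and tested. Under the assumptions above, removal is the usual outcome when the true effect is zero or 0.3 SD and remains common at 0.5 SD. When the term survives at a true 0.3 SD, the estimate averages roughly 1.6 to 2 times the truth (0.47/0.3 to 0.60/0.3). At 0.8-0.9 SD the distortion is small.

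The structural point depends on the wording and on raw NPI scores being the response. The percentages depend also on the assumed correlation, normality, complete data and equal allocation. The damage is to the estimate and interval of a secondary endpoint, not to the type I error of the composite test when removal counts as non-rejection. It should be corrected, but it does not threaten the trial.

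**What to change.** In Section 17, H2a, state that visit, group and visit-by-group are always retained and that any AIC selection applies to baseline covariates only. Add that the between-group difference in change at each follow-up will be reported with its confidence interval, whatever its size. Naming the covariates in advance would be a useful extra but is not essential.

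The cost is two sentences. No new data are needed, and neither the sample size nor the 5% test decision changes. With the design terms forced in, the joint 2-df test rejected in 4.6% to 5.4% of simulated null trials, consistent with 5%.

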4. STUDY DESIGN

This is a Stage 0 study for mechanistic understanding. We will recruit older adults with study partner-rated NPS that has worsened in the past 2 years. Our previous study shows that this will capture

the most detrimental type of NPS.¹ We will focus on the MCI group, since understanding and modifying NPS among this group may assist in slowing the progression of dementia. See Table 1 for the overview of assessment and intervention timeline.

- Double-blind randomized controlled trial of 40 participants and their study partner subjects; all eligible and interested intervention subjects will be enrolled and undergo a baseline assessment, MRI scan, and blood draw; PI, staff conducting follow-up assessments and intervention subjects and their study partner subjects will be blinded. Interventionists and data managers will know randomization.
- After baseline, all intervention subjects will be randomly assigned to one of two groups - active anodal or sham C3 tDCS. A MATLAB block-based randomization code will be used to randomly assign study ID to group. Each study ID-group pairing will be printed and placed inside a sealed envelope labeled with only the study ID to ensure blinding. After an intervention subject and their partner subject finish baseline assessments, the interventionist or data manager will open the randomization envelope to assign the respective study ID.
- All intervention subjects will undergo a total of fourteen (14) 20-minute tDCS sessions over the course of four weeks: ideally, five times a week for two weeks, followed by twice a week for an additional two weeks. However, we will extend the intervention for additional two weeks for make-up sessions.
- Assessments will occur at baseline, within 2-week after finishing intervention (post-intervention assessment), and 4 to 6 weeks after post-intervention assessment (follow-up assessment).
- Unblinding will occur upon the completion of the follow-up assessment. We will not provide those in the sham group with the active tDCS procedure.

Primary endpoints:

- Resting-state and visual attention task-related fMRI;⁴⁵

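### H2a names only a random participant effect for the repeated NPI measures, which implies equal correlation between all visits; if that fails, the standard errors of the 4- and 8-week changes can be wrong

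*Combined protocol and SAP*

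**What the plan says.** Section 17, Aim 2 (H2a) specifies a linear mixed model whose response vector "represents the NPI measures across time". On the mean structure it says: "The models will include fixed effects such as data collection visit (categorical variable), group, visit and group interaction, and covariates identified as being imbalanced". On covariance it says: "A random participant-specific effect will be included to account for correlation between visits for the same participant". The design matrix for this part is introduced in general notation as a "matrix for the random effects" with q columns. No distribution is given for the random effects or the residuals. The section names no residual covariance, variance by visit, random slope, robust standard error, degrees-of-freedom method or covariance sensitivity analysis.

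Two outputs are planned. The first is descriptive: "The model-based average within-group change will be computed for each outcome at 4 and 8 weeks". The second is the between-group test: "We will conduct a composite hypothesis test to assess if the changes at 4 or 8 weeks differ by groups".

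On timing, Section 4 says: "Assessments will occur at baseline, within 2-week after finishing intervention (post-intervention assessment), and 4 to 6 weeks after post-intervention assessment (follow-up assessment"). Section 8 uses screening data as baseline data for eligible participants, and the full NPI is given to the study partner at secondary screening. It adds: "Baseline assessments need to be scheduled within one month of in-person cognitive screening". Treatment then starts within two weeks. It lasts four weeks, with up to two make-up weeks (Section 4.2.2). Table 1 lists the full NPI at in-person screening, immediate post-intervention and final post-intervention, so the model has three visits.

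**The concern.** A random intercept with independent, equal-variance residuals gives the covariance matrix compound symmetry: one variance, and one correlation shared by baseline and post-intervention, baseline and follow-up, and post-intervention and follow-up. The model then uses the same variance for every change between two visits, a pooled average over the three pairs.

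Two features of the trial make equality doubtful. First, the visits are not alike in spacing or in what happens between them. The longest permitted gap from the baseline NPI to the post-intervention NPI is about 14 weeks (about 4 to the baseline assessment, 2 to the start of treatment, 6 of treatment, 2 to the assessment), and the shortest is about 4. That gap contains the whole intervention. The gap from post-intervention to follow-up is 4 to 6 weeks without treatment. Second, entry requires at least two current symptoms with recent worsening (Section 5), which may alter the spread of scores at baseline relative to later visits.

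At stake is the precision attached to the 4- and 8-week changes. Section 17 says that the pilot is meant to inform effect-size calculation for a later trial, so a misstated variance of change could carry over into that trial's sample size.

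**Working it through.** The documents give no SD, between-visit correlation, standard error or power for H2a, so there is no figure of the plan to reproduce.

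**Inputs from the documents.** Three NPI visits; 40 participants and 10% attrition (Section 17), so 40 × 0.9 = 36 completers; alpha 0.05.

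**Assumptions.** Equal allocation (18 per arm), two-sided testing, complete data, and every correlation and SD below.

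**Formula.** For complete balanced data the variance of a change between visits i and j is V(i,j) = σᵢ² + σⱼ² − 2σᵢⱼ. The random-intercept model estimates one within-participant variance, and the variance that it uses for any change is the mean of the three V(i,j). Hence

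model SE / true SE for baseline to visit j = √(mean of the three V / V(baseline, j)).

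The ratio does not depend on the sample size. With unit variances, V = 2(1 − ρ).

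**Standard errors.** Correlations are in the order baseline–post, baseline–follow-up, post–follow-up, and V is in the same order.

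| Correlations | V | Mean V | Ratio at post | Ratio at follow-up |
|---|---|---|---|---|
| 0.5 / 0.5 / 0.5 | 1.0, 1.0, 1.0 | 1.0 | 1.00 | 1.00 |
| 0.6 / 0.5 / 0.6 | 0.8, 1.0, 0.8 | 0.867 | √(0.867/0.8) = 1.04 | √(0.867/1.0) = 0.93 |
| 0.5 / 0.4 / 0.75 | 1.0, 1.2, 0.5 | 0.9 | √(0.9/1.0) = 0.95 | √(0.9/1.2) = 0.87 |
| 0.4 / 0.3 / 0.8 | 1.2, 1.4, 0.4 | 1.0 | √(1.0/1.2) = 0.91 | √(1.0/1.4) = 0.85 |
| 0.7 / 0.49 / 0.7 (autoregressive) | 0.6, 1.02, 0.6 | 0.74 | √(0.74/0.6) = 1.11 | √(0.74/1.02) = 0.85 |

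**False-positive rates.** These come from 40,000 simulated null trials per pattern at 18 per arm, nominal 5%. Where two independent runs differed, both results are shown.

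| Correlations | Contrast at post | Contrast at follow-up | Composite test |
|---|---|---|---|
| Equal, 0.5 | about 5% | about 5% | about 5% |
| 0.6 / 0.5 / 0.6 | 4.2% | 6.6% | 5.0–5.2% |
| 0.5 / 0.4 / 0.75 | 6.2–6.5% | 8.8–9.0% | 5.8–6.0% |
| 0.4 / 0.3 / 0.8 | 7.5% | 9.9–10.0% | 6.6% |
| Autoregressive 0.7 | 3.0–3.2% | 9.4–9.5% | 5.5% |

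The contrast columns are between-group differences in change. The within-group changes showed the same rates.

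**Unequal variances as well.** These patterns widen the range:
- SDs 1/1.3/1.3 with all correlations 0.6: ratio 1.03 at both visits, slightly conservative throughout.
- SDs 1/0.8/0.7 with 0.6/0.5/0.8: ratios 0.91 and 0.85, composite 6.5%.
- SDs 1/1.2/1.4 with autoregressive 0.6: ratios 1.20 and 0.86, composite 5.6%.

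**Carry-over to a later trial.** In the last three rows of the first table, the model's variance of the follow-up change is 0.9/1.2 = 0.75, 1.0/1.4 = 0.71 and 0.74/1.02 = 0.73 of the truth, an understatement of 25%, 29% and 27%. In the 0.6/0.5/0.6 row it is 0.867, an understatement of 13%.

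**Check of the remedy.** With an unstructured covariance (a t-test on each change, Hotelling's T² for the composite), the simulated error was 4.7–5.2% for each contrast and 4.8–5.2% for the composite in every pattern of the independent check, at 18 and at 20 per arm.

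**The case against.** The strongest reply is that the plan is silent rather than wrong. The number of random effects is left general, the residual covariance is not stated, and a participant effect is said to be included, not to be the sole term. This stands in part: a reader might infer that the plan forces compound symmetry, and the text does not go that far. But the participant effect is the only covariance term named, a random intercept is its plain reading, and if something else was meant, the plan still needs to say so.

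The same paragraph introduces the models as being for changes in NPS. If the response held the two change scores, equal correlation would impose nothing, and only equal variance of the two changes would be assumed. The definition of the response as NPI measures across time, with change then derived from the model, points to visit-level scores.

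A reader might also infer that the intervals will be too narrow. The documents do not support this. They contain no NPI correlations or SDs, the error is zero under equal variances and correlations, and the post-intervention error goes either way. The schedule argument rests partly on maximum windows; at the short end the two gaps can be similar.

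The higher error rates belong to separate contrasts at each visit. The plan's stated between-group test is the composite one, and the within-group changes are meant to rank the groups. This stands, and it limits the consequence. NPI is also a secondary endpoint, and the sample size does not use this model. Finally, the simulations omit attrition, covariates and the planned stepwise selection, so the percentages are illustrative.

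**Conclusion.** The point holds as a cheap improvement to an under-specified analysis. It does not show that the planned between-group inference is invalid. Read plainly, H2a assumes equal variance and equal correlation over three visits whose spacing and content make exact equality doubtful, and nothing in the plan relaxes or checks this.

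Under the four unequal-correlation patterns with equal variances, the model SE is about 0.91 to 1.11 of the true SE at post-intervention and 0.85 to 0.93 at follow-up. The separate-contrast error is about 3 to 7.5% and 6.6 to 10%. The composite test stays at about 5 to 6.6%. The consequence therefore falls mainly on the reported 4- and 8-week changes, their intervals, and any variance of change taken from the model to size a later trial. These sizes rest on assumed correlations, complete data and equal allocation.

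**What to change.** Replace the random intercept for H2a with an unstructured covariance over the three NPI visits, fitted with Kenward-Roger degrees of freedom, and state that the response is the visit-level NPI score.

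Name the fallback in advance, for use only if that model does not converge. It should not impose one common correlation, which rules out heterogeneous compound symmetry. Suitable choices are heterogeneous Toeplitz or heterogeneous AR(1), or a random intercept with small-sample-corrected robust standard errors. The first two still tie the baseline–post correlation to the post–follow-up correlation, so the robust option is the more general.

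The cost is SAP wording and up to four more variance parameters (six for an unstructured 3 × 3 matrix against two for a random intercept), with a small loss of degrees of freedom if the correlations are in fact equal. No new data are needed, and the sample size does not change.
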